#### Providing assistance to the user

If the user is able to successfully administer the dose but requires your help to complete the injection, document the specifics below, including asking the user if after the injection they are now confident that they will be able to inject unassisted at home.

If not, provide additional training until you have addressed their confusion or concerns and they confirm their understanding as to how to successfully administer the study drug.

Turn over for questions 

Effective Date: Date of final electronic approval

### Observer Questionnaire

Turn over for instructions 

Subject ID

Assessment date

Pen kit number

Signature:

**1** Based on your observations, did the user successfully inject into an acceptable injection site? Please report all injections from this pen.

**Injection 1**

Yes

No

**Injection 2**

Yes

No

**Injection 3**

Yes

No

1. VERSION HISTORY

Table 1. Summary of Changes

Version/ Date	Associated Protocol Amendment	Rationale	Specific Changes
V1	No separate CP-4-006 (C0311009) OLE protocol. Referring to Section 5.3 study procedure for LT-OLE and sub-section of OLE embedded in each section of the Amendment V5.0 dated 2 May 2018	Original SAP	No

2. INTRODUCTION

Human growth hormone (hGH) is a 191-amino-acid pituitary protein that stimulates hepatic production and release of insulin-like growth factor-1(IGF-1) into the systemic circulation. IGF-1 is an important mediator in the promotion of linear growth in children and may play a role in the regulation of metabolism and body composition in adults. These factors are regulated through complex feedback mechanisms involving hGH, IGF-1 binding protein-3 (IGFBP-3) and their complexes.

The majority of currently available hGH products require daily or every other day subcutaneous (SC) or intramuscular (IM) injections to maintain hGH blood levels within the effective therapeutic window. The burden of daily administration and its concomitant side effects (e.g., injection site discomfort, transient edema and arthralgia) cause a reduction in compliance (Rosenfeld and Bakker 2008²) and can limit the therapeutic utility of existing formulations.

Somatrogon is a long-acting r-hGH for SC administration. It consists of hGH fused to three copies of the C-terminal peptide (CTP) of the beta chain of human chorionic gonadotropin; one copy at the N-terminus and two copies (in tandem) at the C-terminus. Somatrogon is the International Nonproprietary Name (INN) of somatrogon and can be used interchangeably with MOD-4023.

The purpose of the current Phase 3 study is to demonstrate that weekly somatrogon administration in pre-pubertal children with growth hormone deficiency (GHD) is clinically non-inferior to daily Genotropin® administration in terms of safety and efficacy after 12 months treatment duration. The study will be conducted in a randomized, open-label, active-controlled, parallel-group design. After completion of an initial 12-month treatment, patients will be eligible to continue treatment with weekly somatrogon in a single arm, long-term

open-label extension (LT-OLE) study for the purpose of collecting additional long-term safety and efficacy information.

As the dose selection is driven by evaluating the annual increment in height velocity (HV), the annual HV data obtained for somatropin was compared to Genotropin® results in the Phase 2 study for 52 patients (one patient was mis-diagnosed). Based on 12-month auxology data, it is most likely that a minimum somatropin dose of 0.66 mg/kg/wk will provide an annualized HV comparable to daily hGH at a dose of 34 µg/kg/day.

This SAP provides the detailed methodology for summary and statistical analyses of the OLE data collected in Study CP-4-006 (████████). This document may modify the plans outlined in the protocol; however, any major modifications of the primary endpoint definition or its analysis will also be reflected in a protocol amendment.

2.1. Study Objectives, Endpoints, and Estimands

LT-OLE Objective:

To assess the long-term efficacy, safety, and immunogenicity of somatropin in the LT-OLE period.

2.1.1. Estimand(s)

The estimand of this study uses the treatment policy strategy and estimates the effect for all participants treated regardless of whether an intercurrent event occurs. Each of them includes the following four attributes:

- Population: All patients who entered OLE period and had at least one dose of somatropin;
- Variable:
 - Annualized height velocity (AHV) at each 12-month interval (cm/year)
 - Height standard deviation score (SDS) and change in height SDS;
 - Change in bone maturation (BM);
 - IGF-1 and IGF-1 SDS levels on day 4 (-1) after somatropin dosing across study visits;
 - IGFBP-3 levels and IGFBP-3 SDS on day 4 (-1) after somatropin dosing across study visits;
 - Pubertal status (according to Tanner stages);
 - For males that are 13 years and older: luteinizing hormone (LH), follicle-stimulating hormone (FSH) and testosterone;

- For females that are 12 years and older: LH, FSH and estradiol
- Intercurrent event: All data after an intercurrent event (discontinuation of treatment, discontinuation of study, etc.), if collected, will be included;
- Population-level summary: descriptive summary for absolute values at each visit and/or change from previous interval.

2.1.2. Additional Estimand(s)

Not Applicable.

2.2. Study Design

The study will be divided into two parts: Main Study Period (main study) and OLE Period.

The main study will consist of 12 months, open-label, multi-center, randomized, active controlled, parallel group study comparing efficacy and safety of weekly somatropin to daily GH, Genotropin®. Both drugs will be injected using a PEN device.

Patients who received somatropin during the main study will continue in the LT-OLE with the same dose (mg/kg/wk) of somatropin. Patients who received Genotropin® during the main study will be switched to somatropin and will begin treatment with a dose of 0.66 mg/kg/wk beginning no less than one day after cessation of Genotropin® treatment.

The key safety data will be reviewed by an independent Data Safety Monitoring Board (DSMB) approximately every 6 months. During the entire study (main study and LT-OLE), the dose of somatropin and Genotropin® will be adjusted every 3 months based on the patient's body weight. Doses may be decreased for safety reasons according to the pre-defined dose-adjustment criteria (which will be based on the severity of adverse events (AEs) or repeated, elevated levels of IGF-1). The dose will be decreased based on two, repeated day 4(-1) post-dose levels of IGF-1 SDS $> +2.0$. During the LT-OLE, dose reduction for IGF-1 level $>+2.0$ SDS will be made following consultation with the Global Study Medical Monitor on an individual patient basis.

The LT-OLE will continue until marketing approval.

3. ENDPOINTS AND BASELINE VARIABLES: DEFINITIONS AND CONVENTIONS

3.1. Efficacy Endpoints

3.1.1. Annualized Height Velocity (cm/year)

AHV at each 12 month is based on the difference between the height (HT) at each 12 month and the height at the previous 12 month.

$$\text{HT at Month 12 of current year} - \text{HT at Month 12 of prior year}$$

AHV(cm/year) = -----
(Month 12 Visit Date of current year – Month 12 Visit Date of prior year) / 365.25

The following algorithm will be used in case the reference visit (i.e., previous 12 month visit) is missing:

- If main period Month 12 (OLE Baseline), Visit 16 (OLE Month 12), Visit 20 (OLE Month 24), Visit 24 (OLE Month 36) are not missing, these will serve as reference visits.
- If missing, create anchor visit which is the scheduled visit (non-missing) prior to the missed reference visit, or scheduled or unscheduled visit (non-missing) after the missed reference visit based on the anchor logic described below:
 - A subject showed a missing reference visit at visit 16
 - This subject completed Visit 15 (OLE Month 9; Anchor A) and Visit 17 (OLE Month 15; Anchor B) and did not complete an Unscheduled Visit. One of the scheduled visits (non-missing) will be determined as the Anchor Visit
- Anchor logic:
 - If Anchor B – Anchor A < 6 months (180 days) then Anchor A will be used as the reference visit.
 - If Anchor B – Anchor A \geq 6 months (180 days) then Anchor B will be used as the reference visit.
 - If a reference visit was performed out of window and reported as an unscheduled visit then unscheduled visit will be used as the reference visit, Anchor C.

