- Positive urine pregnancy test or confirmed pregnancy. In case of pregnancy, the study drug should be discontinued, and the Global Study MM be alerted immediately. All pregnancy tests used in this study, either urine or serum, must have a sensitivity of at least 25 mIU/mL and must be performed by a certified laboratory. Pregnancy tests will also be done whenever one menstrual cycle is missed during treatment (main study and LT-OLE) and when potential pregnancy is otherwise suspected and may be repeated if requested by institutional review boards (IRBs)/ethics committees (ECs) or if required by local regulations. In the case of a positive confirmed pregnancy, the patient will be withdrawn from administration of investigational product but may remain in the study for follow up.
- When the patient's annualized growth rate is  $\leq 2$  cm/12 months (the interval between two height measurements should be at least six months).

Patients can be re-screened for inclusion in the main study **one** time. Any data collected during the original screening period will be acceptable as historical data, EXCEPT safety laboratory data and IGF-1 and IGFBP-3 levels, which must be repeated and evaluated for eligibility. In this case, the patient will be assigned a new screening number.

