#### 8.4.7 Auxology/Clinical Endpoints

- Annual HV in cm/year at each 12-month interval.

- Change in height SDS every 12 months (compared to the previous values).
- Change in bone maturation (BM) every 12 months, (compared to Week 52 BA (calculated as BA/CA) at completion of LT-OLE year 1 and to previous values from LT-OLE year 2 onwards).

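### When an annual visit is missed, SAP 3.1.1 picks the substitute reference height by the gap between the neighbouring visits, not by closeness to the due date, so after consecutive misses an annual height velocity can cover 26 or 13 weeks

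*SAP*

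**What the plan says.** Protocol 8.4.7 defines the extension endpoint as "Annual HV in cm/year at each 12-month interval". SAP 3.1.1 agrees: "AHV at each 12 month is based on the difference between the height (HT) at each 12 month and the height at the previous 12" months, divided by the elapsed time in years of 365.25 days.

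If the earlier of the two annual visits is missing, SAP 3.1.1 substitutes another visit. The first candidate comes from the instruction to "create anchor visit which is the scheduled visit (non-missing) prior to the missed reference visit" (Anchor A). The second is a "scheduled or unscheduled visit (non-missing) after the missed reference visit based on the anchor logic described below" (Anchor B). The choice between them rests on one comparison. If B minus A is below the cut-off of "6 months (180 days) then Anchor A will be used as the reference visit". If it is at or above the cut-off of "6 months (180 days) then Anchor B will be used as the reference visit". An annual visit made out of window and recorded as unscheduled is used directly (Anchor C).

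The SAP illustrates the rule with Visit 16 missing, Visit 15 as Anchor A and Visit 17 as Anchor B. SAP 5.3 refers back to this section for a missing reference value and adds nothing. SAP 6.1.2 plans no sensitivity analysis.

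**The concern.** A substitute for a missed annual height should stand as near as possible to the date when that height was due, so that the velocity still describes about one year. The SAP criterion does not measure this. It measures how far apart the two candidates are, and it sends the choice to the later visit when the gap is long. A long gap usually means that visits after the due date were also missed, and then the later candidate is the poorer one.

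Three safeguards are also absent: a latest date for B, a minimum span for the velocity, and a statement that B must come before the current annual visit.

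Annualized height velocity is the first variable listed in the SAP estimand (2.1.1), and SAP 5.3 calls it the primary endpoint. A value from a short span does not average growth over a year and magnifies height-measurement error, yet it would enter the same yearly mean as true 12-month values. The children affected are those with missed visits.

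**Working it through.** **Inputs.** Nominal weeks from Protocol 5.3.3 and Appendix A: Visit 15 = 91 (±2), Visit 16 = 104 (±4), Visit 17 = 117 (±2), Visit 18 = 130 (±2), Visit 19 = 143 (±2), Visit 20 = 156 (±4). The cut-off of 180 days is from SAP 3.1.1.

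**The plan's own figures.** Six months on the SAP's year is 365.25 / 2 = 182.6 days, close to the stated 180. In the SAP's example the gap is (117 − 91) × 7 = 182 days. This is at least 180, so B is used.

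**Applying the rule to Year 2 (Visit 16 missed, Visit 15 done).** Gap = (week of B − 91) × 7. Span = 156 − week of B. Anchor A is always 104 − 91 = 13 weeks from the due date.

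| Also missed | B | Gap (days) | Rule takes | B to due date (weeks) | Nearer visit | Span to Visit 20 |
|---|---|---|---|---|---|---|
| none | Visit 17 | 182 | B | 13 | tie | 39 weeks (273 days) |
| Visit 17 | Visit 18 | 273 | B | 26 | A | 26 weeks (182 days) |
| Visits 17–18 | Visit 19 | 364 | B | 39 | A | 13 weeks (91 days) |
| Visits 17–19 | Visit 20 | 455 | B | 52 | A | 0 (formula gives 0/0) |

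In the last three rows A would give 156 − 91 = 65 weeks (455 days, about 15 months). Across the visit windows the 26-week span runs from (152 − 132) × 7 = 140 to (160 − 128) × 7 = 224 days. The 13-week span runs from (152 − 145) × 7 = 49 to (160 − 141) × 7 = 133 days.

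The same spans arise for Year 1 if the Visit 8/10 height is missing, with Visit 7 (week 39) as A and Visits 13 to 16 as B. This takes B as the next visit with a height; the SAP does not say so, and Visits 11 and 12 have no height measurement in Appendix A.

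**Sensitivity in the single-miss case.** A gap of 179 instead of 182 days switches the reference from B to A and the span from about 9 to about 15 months. Taking every pair of days for Visits 15 and 17 in their ±2-week windows as equally likely (an assumption; 29 × 29 = 841 pairs):
- A is chosen in 351 (42%).
- The visit farther from the due date is chosen in 406 (48%), the nearer in 48%, and 3% are ties.
- Where the farther visit is chosen, it is farther by 10 days on average and by 28 at most.

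**Measurement error.** With height-error SD s at each visit, the error SD of the velocity is s × √2 / (span in years). The ratio of a 13-week to a 52-week span is 52 / 13 = 4 for any s. The documents give no s; for assumed values:

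| s (cm) | 65 weeks | 52 | 39 | 26 | 13 |
|---|---|---|---|---|---|
| 0.1 | 0.11 | 0.14 | 0.19 | 0.28 | 0.57 cm/year |
| 0.2 | 0.23 | 0.28 | 0.38 | 0.57 | 1.14 |
| 0.3 | 0.34 | 0.43 | 0.57 | 0.85 | 1.70 |

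**The case against.** Several points against this stand.

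- **The common case is mild.** With one missed visit both candidates lie about 13 weeks from the due date, and the formula divides by actual elapsed time, so 9- and 15-month values remain rates in cm/year. The 48% might be read as showing that the rule does serious harm half the time. It does not, because the two visits are then nearly equidistant. With s = 0.3 and the protocol's between-patient SD of 2.5 cm/year, moving from 52 to 39 weeks raises the total SD only from √(2.5² + 0.43²) = 2.54 to √(2.5² + 0.57²) = 2.56.
- **The extreme cases need consecutive misses.** The 13-week span needs three missed visits in a row and the zero span four. Drug is dispensed at each of them, and a programmer would probably notice a division by zero. A reader might infer that annual velocities will routinely rest on three months or on nothing; the documents do not support that.
- **The protocol does not bar short spans for the endpoint.** Protocol 4.4 says that "the interval between two height measurements should be at least six months", but this belongs to a withdrawal criterion. Elsewhere the protocol annualizes over shorter spans: 8.4.1 extends the formula to any post-baseline visit, 8.4.2 has a 6-month velocity, and 8.6.5 uses the last available height for children who discontinue. The SAP rule therefore breaches no endpoint rule in the protocol.
- **A 15-month span does not count growth twice.** If Visit 16 is missing, the Year 1 velocity is itself missing, because SAP 5.3 does not impute it. The longer span brings prior-year growth into the current year, which is a lesser fault.
- **A nearest-visit rule has its own edge.** Visits 15 and 17 on schedule tie exactly, so a one-day shift would also switch the reference unless a tie-break is given.

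None of this defends choosing B when it is 26, 39 or 52 weeks from the due date and A is 13.

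**Conclusion.** The point holds in a limited form. The selection rule is fully stated and uses the wrong criterion. With one missed visit the consequence is modest: a span of about 9 or about 15 months, decided by a few days of scheduling. With two or more consecutive misses starting at the annual visit, the rule takes the more distant height and shortens an annual velocity to about 26 or 13 weeks; on a literal reading it can select the current visit as its own reference. The 13-week value carries four times the annualized measurement-error SD of a 52-week value.

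The extension has no hypothesis test (SAP 5.1), so no error rate or sample size is affected. What suffers is the meaning and precision of the reported annual velocity. How many children are affected cannot be derived from the documents. The spans rest on nominal visit weeks, the percentages on uniform timing within windows, and the error SDs in cm/year on assumed height errors of 0.1 to 0.3 cm. The rule should be changed before the extension data are analysed.

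**What to change.** Replace the A/B logic in SAP 3.1.1 and keep Anchor C:

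1. Use the non-missing height, scheduled or unscheduled, closest to the due date of the missed reference visit and strictly before the current annual visit.
2. State a tie-break, since Visits 15 and 17 on schedule are equidistant.
3. With a substituted reference, derive the velocity only if the span lies in a stated range, given in days. Otherwise set it to missing and list it with its interval. The range should not cut through the ordinary single-miss case. The 6 to 18 months that Protocol 4.1 uses for height velocity at entry would do: under nearest-visit selection the single-miss spans run from 231 to 497 days, all inside it. A range of 9 to 15 months would exclude about 41% of single-miss children (Visits 15, 17 and 20 uniform in their windows, ties split evenly).
4. Say how the range relates to the last-available-height provision of Protocol 8.6.5, so that the two do not conflict for children who discontinue.
5. Say what happens when the extension-baseline height is missing. Anchor A is then Visit 7, which would bring about three months of main-study Genotropin growth into the Year 1 velocity of switched children.

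The cost is a paragraph of SAP text and a small programming change. A few children with long gaps lose a value, and some spans will run to about 15 months and include prior-year growth.

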3.1.2. Change in Height SDS

Height SDS will be calculated as the Z-score using LMS method as:

$$Z = [((\text{Height} / M)^L) - 1] / (S * L),$$

where L, M, S will be determined from the age and gender standards listed in 2000 CDC Growth Charts (www.cdc.gov/growthcharts) for age 2 to 20, or CDC reference datasets.

Change in height SDS will be calculated as the difference between the height SDS at each scheduled visit in OLE period and the height SDS at the main period baseline.

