#### 8.6.5 LT-OLE Analysis

During the LT-OLE the primary goal of this safety and efficacy analysis is to report on the effect of long-term treatment on Annual HV and other auxological/clinical and biochemical measures.

- Annual HV will be summarized with descriptive statistics each year of LT-OLE treatment. For patients who discontinue without annual measurement, their HV will be calculated based on their last available measure.
- Change in Ht SDS every 12 months (the last value within each year compare to the value 12 months earlier) will be summarized with descriptive statistics.
- Change in bone maturation (BM) every 12 months, (compared to Week 52 BA (calculated as BA/CA) at completion of LT-OLE year 1 and to previous values from LT-OLE year 2 onwards).
- IGF-1, IGF-1 SDS, IGFBP-3 and IGFBP-3 SDS will be summarized with descriptive statistics at each visit. A summary of the incidence of IGF-1 SDS >2.0 at each visit will be provided.

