3.2.2. IGF-1 (ng/mL) and IGF-1-SDS

IGF-1 levels and IGF-1 SDS will be measured and calculated on day 4 (-1) after somatrogon dosing across study visits in OLE at every scheduled visit in OLE period. Change in IGF-1 SDS at each visit will be calculated as the difference between the IGF-1 SDS values in the OLE period and the IGF-1 SDS at the main period baseline.

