3.2.3. IGFBP-3 (ng/mL) and IGFBP-3-SDS

IGFBP-3 levels and IGFBP-3-SDS will be measured and calculated on day 4 (-1) after somatrogon dosing across study visits in OLE at every scheduled visit in OLE period. Change in IGFBP-3 SDS at each visit will be calculated as the difference between the IGFBP-3 SDS values in the OLE period and the IGFBP-3 SDS at the main period baseline.

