3.4. Baseline Variables

Baseline is defined as the main period baseline for efficacy and biomarker assessment. Except the reference visit for AHV, is defined in Section 3.1 as the values at the previous 12 month in the OLE period.

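### The SAP defines extension-period change in height SDS only from the pre-treatment main-study baseline, not over each 12 months as in the protocol, so for switched children it includes the whole Genotropin year

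*SAP*

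**What the plan says.** **Protocol.** Section 8.4.7 gives the extension endpoint as "Change in height SDS every 12 months (compared to the previous values". Section 8.6.5 describes the analysis as "the last value within each year compare to the value 12 months earlier". The synopsis lists the same endpoint.

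**SAP.** Section 3.1.2 takes the change as the difference between "the height SDS at each scheduled visit in OLE period and the height SDS at the main period baseline". Section 3.4 generalizes this: "Baseline is defined as the main period baseline for efficacy and biomarker assessment". The only exception is annualized height velocity, which is referred to the previous 12-month visit. Section 6.1.1 then summarizes change from baseline to each extension year, and allows presentation by randomized arm and in total.

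The estimand section (2.1.1) gives the summary measure as "descriptive summary for absolute values at each visit and/or change from previous interval". That fits the protocol but not SAP 3.1.2 or 3.4.

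**Treatment sequence.** SAP 2.2: "Patients who received Genotropin® during the main study will be switched to somatropin" (the text prints somatropin where somatrogon is meant). These children therefore have 12 months on the comparator before their first somatrogon dose. The objective in SAP 2.1 is long-term efficacy of somatrogon in the extension.

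**The concern.** The two documents define the same-named endpoint with different reference points. The protocol's version measures what happened in the last year. For a switched child in extension Year 1, that is the year on somatrogon. The SAP's version measures everything since before any GH treatment. For a switched child, that includes the complete response to the comparator.

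At stake is whether the defined change speaks to the stated objective. A switched child whose height SDS stayed level on somatrogon would still show the whole Genotropin-year gain as change from baseline at every extension visit. In a pooled total, the first-year component comes from somatrogon in one arm and from Genotropin in the other. The SAP reserves the right to modify the protocol, but it neither mentions nor justifies this modification, and its own estimand wording points the other way.

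**Working it through.** No figure in the plan depends on this definition, so there is nothing to reproduce first.

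**1. Decomposition.** For any child with both values observed:

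change from main baseline = (main Month 12 − main baseline) + (extension visit − main Month 12)

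For a switched child the first bracket is the Genotropin year and the second is the somatrogon period. The protocol's change for extension Year 1 is the second bracket alone. From Year 2 on, it is the change since the prior annual visit.

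**2. Share of the interval spent in the Genotropin year.** Inputs: the main period ends at week 52, and extension visits fall at the study weeks in protocol Appendix A (week 208 = 156 + 52). Under the SAP the share is 52 / study week.

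| Study week | SAP reference: 52 / week | Protocol 12-month reference |
|---|---|---|
| 65 | 80% | not an annual visit |
| 78 | 67% | not an annual visit |
| 91 | 57% | not an annual visit |
| 104 | 50% | 0% |
| 156 | 33% | 0% |
| 208 | 25% | 0% |

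These are shares of time and need no assumption about growth. They ignore visit windows and any delay between the periods.

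**3. Illustration in SDS units (assumed values).** The documents give no height SDS gains. Assume 0.5 to 1.0 SDS in the Genotropin year and 0.2 to 0.5 SDS in extension Year 1.

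- SAP definition at week 104: 0.5 + 0.2 = 0.7 up to 1.0 + 0.5 = 1.5.
- Protocol definition: 0.2 to 0.5.
- Ratio: lowest (0.5 + 0.5) / 0.5 = 2.0; highest (1.0 + 0.2) / 0.2 = 6.0.
- Part gained on Genotropin: lowest 0.5 / 1.0 = 50%; highest 1.0 / 1.2 = 83%.

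**4. Can the 12-month change be recovered from the other displays?** Only in part. Subtracting mean height SDS at two visits gives the mean change if the same children contribute to both. SAP 5.3 does not impute and summarizes observed data, so the contributing children can differ. The SD of the within-child change is √(s₁² + s₂² − 2·r·s₁·s₂), and it needs the within-child correlation r, which visit-wise means and SDs do not provide.

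**5. Who is affected.** Randomization is 1:1, so about half of the randomized children are potential switchers. The proportion entering the extension is not known from the documents.

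**The case against.** The strongest replies, and what stands of each:

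- **Growth on somatrogon is isolated elsewhere.** Height velocity in SAP 3.1.1 uses the prior 12-month visit, with main Month 12 as extension baseline, and absolute height SDS is shown by visit and arm. This stands as mitigation. But height velocity is in cm/year and is not standardized for age and sex, so it cannot stand in for the height SDS endpoint.
- **Change since the start of treatment is a legitimate long-term measure.** It is, and for children always on somatrogon it is a natural one. The difficulty is that it is the only change in height SDS the SAP defines.
- **The SAP may modify the protocol, nothing is tested, and the list of summary tables is blacked out.** All true. Annual-change tables may exist. The definitions still conflict and would govern whatever is programmed. The table list also uses the word total for pooling across antibody status, so the pooled-arm point rests on SAP 6.1.1.
- **Main Month 12 is not a perfect starting point.** Protocol 5.3 allows a gap before extension dosing, and height is not among the assessments listed for repeat after a gap of more than 90 days. This calls for a footnote. It does not favour a reference a year further back.

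Three stronger readings are tempting but not supported.

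- **That the same defect affects IGF-1 and IGFBP-3 SDS.** SAP 3.2.2 uses "the difference between the IGF-1 SDS values in the OLE period and the IGF-1 SDS at the main period baseline" and SAP 3.2.3 uses the same reference. But these are current levels sampled after somatrogon dosing, so no accumulated Genotropin gain is carried forward. Protocol 8.4.8 and 8.6.5 ask for levels by visit and define no 12-month change, so there is no departure either.
- **That the SAP's change could never show waning.** The reference is fixed for each child and change is computed at every scheduled visit, so a decline during the extension would appear as a falling change.
- **That the SAP presents the figure as a somatrogon-only gain.** It calls it change from baseline.

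**Conclusion.** The point holds for height SDS. SAP 3.1.2 and 3.4 depart from protocol 8.4.7 and 8.6.5 without saying so, and they conflict with SAP 2.1.1. For switched children the defined change spans the full Genotropin year, which is half the interval at week 104 and a third at week 156. That follows from the visit schedule alone. The size in SDS units is not known from the documents; the 2.0- to 6.0-fold difference rests entirely on the assumed gains.

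No hypothesis test or main-study result is affected. What changes is the reported descriptive result for an endpoint named in the protocol. The mitigating displays limit the harm, but they do not supply the within-child 12-month change or its variability.

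**What to change.** - **SAP 3.1.2, 3.4 and 6.1.1:** define the main extension-period change in height SDS as the value at the annual visit minus the height SDS 12 months earlier. The reference is main Month 12 (extension baseline) for extension Year 1 and the prior annual visit after that. This restores the protocol's definition and agrees with SAP 2.1.1.
- **Keep change from main baseline as a supplementary display**, by randomized arm, labelled for switchers as total GH treatment (Genotropin year plus somatrogon).
- **Footnote** any treatment gap between main Month 12 and the first extension dose, and state what is done when the reference height is missing.
- **IGF-1 and IGFBP-3 SDS:** no correction is needed. Change from extension baseline may be added as an optional display.

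The cost is SAP wording and one set of table columns, since height is already measured at Visit 8/10 and at each annual visit. The downside is that the main reported change in height SDS will look smaller. If the sponsor prefers the main-baseline reference as the main change, the SAP should declare and justify the departure.
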